## 9.0 STATISTICAL ANALYSIS

### 9.1 Sample Size Calculation

In the Phase 2, the VERU-111 treated group showed a 5.3% mortality rate compared to a 30% mortality rate in the Placebo group in the same patient population.

Approximately, 210 subjects are planned to be randomized at a 2:1 ratio into two treatment arms (140 subjects in the VERU-111 treated group and 70 subjects in the Placebo treated group). Randomization will be stratified by baseline WHO Ordinal Scale score of 4, 5 and 6 such that subjects with a WHO Ordinal Scale of 4, 5 and 6 at baseline will be approximately equally distributed between the treatment groups. Assuming a rate of mortality of 5% in the VERU-111 treated group and 25% in the Placebo treated group, the above sample sizes will yield 95% confidence interval of [-0.308, -0.092] for the risk difference between treatment groups. Other scenarios are shown in the table below.

$$\text{Confidence interval} = (p_1 - p_2) \pm z^* \sqrt{(p_1(1-p_1)/n_1 + p_2(1-p_2)/n_2)}$$

where:

- $p_1, p_2$ : sample 1 proportion, sample 2 proportion
- $z$ : the z-critical value based on the confidence level
- $n_1, n_2$ : sample 1 size, sample 2 size

Table of Alternative 95% Confidence intervals for the difference between Treatment Groups:  
 Mortality at Day 60

VERU-111	Placebo	Difference	LOWER 95% CI	UPPER 95% CI
0.05	0.15	-0.1	-0.191107629	-0.008892371
0.05	0.2	-0.15	-0.250420118	-0.049579882
0.05	0.25	-0.2	-0.307672652	-0.092327348
0.05	0.3	-0.25	-0.363261644	-0.136738356
0.1	0.15	-0.05	-0.147297482	0.047297482
0.1	0.2	-0.1	-0.206067903	0.006067903
0.1	0.25	-0.15	-0.262958399	-0.037041601
0.1	0.3	-0.2	-0.318297929	-0.081702071
0.15	0.15	0	-0.102449012	0.102449012
0.15	0.2	-0.05	-0.160812454	0.060812454
0.15	0.25	-0.1	-0.21742487	0.01742487
0.15	0.3	-0.15	-0.27256998	-0.02743002

With significance level  $\alpha=0.05$ , and a 2:1 ratio of enrollment into the VERU-111 and Placebo arms respectively, the sample size is adequate to achieve  $>92\%$  power assuming the treatment estimates stated above.

NOTE: The IDMC will monitor efficacy and safety and may make a recommendation to stop the study based on treatment success according to the statistical analysis plan and IDMC charter for this study.

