6.11.5.2 Days in ICU

‘Days in ICU’ will be summarized using descriptive statistics (n, mean, standard deviation, median, minimum and maximum) by treatment group.

‘Days in ICU’ will be the number of days in ICU up to Day 60. In this analysis the worst possible endpoint will be assigned to those subjects who died at any time up to Day 60. For subjects who died the days in ICU will be set to 60. Even for those who were never in the ICU. If

Controlled Quality Management Document			
	Sponsor:	Veru Inc.	
	Protocol Number:	V3011902	
STATISTICAL ANALYSIS PLAN. PHASE 2-3-4			

subject did not report any days in the ICU then their days will be set to zero except for those who died.

Same analysis will be performed in subgroups for region, standard of care and WHO Ordinal Scale at baseline.

A sensitivity analysis will be performed using the actual number of days in ICU. If subject was never in the ICU then days in ICU will be set to 0 even if subject died.

Treatment comparison will be based on analysis of covariance (ANCOVA) model including treatment as a factor, and study site (or country or region), remdesivir use (No/Yes), dexamethasone use (No/Yes) and WHO Ordinal Scale strata used in randomization as covariates. Treatment difference, standard error, 95% confidence interval and p-value will be presented.

Example SAS codes for the analysis are as follows:

```
proc mixed data=XXX order=internal;
  class trt01pn site remdesivir dexamethasone;
  model response=trt01pn site remdesivir dexamethasone whostrata /
    ddfm=kr;
  lsmeans trt01pn / cl diff;
  ods output tests3=tests lsmeans=lsmeans diff=diffs
  run;
```

6.11.5.3 WHO Ordinal Scale for Clinical Improvement change from baseline to Day 15, Day 22, and Day 29

WHO Ordinal Scale for Clinical Improvement will be summarized in frequency table by visit and treatment group.

Additionally, response status for each subject will be defined based on WHO Ordinal Scale for Clinical Improvement. This analysis will compare subjects that have WHO score 0 or 1 (responder) on the visit to subjects who have WHO score ≥ 2 (non-responder) on the visit.

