6.11.5.4 Days on mechanical ventilation

Mechanical ventilation is defined as subject having ‘Intubation and mechanical ventilation’ or ‘Ventilation + additional organ support – pressors, RRT, ECMO’.

‘Days on mechanical ventilation’ will be summarized using descriptive statistics (n, mean, standard deviation, median, minimum and maximum) by treatment group.

‘Days on mechanical ventilation’ will be defined using two different algorithms similarly to ‘Days in ICU’.

‘Days on mechanical ventilation’ will be analyzed using the same methodology as for ‘Days in ICU’ and the same sensitivity analysis will be performed.

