6.11.7 Multiplicity

Holm (1979) step-down procedure will be used to control multiplicity for selected key secondary endpoints (days in ICU and days on mechanical ventilation).

If the primary analysis of the primary endpoint is significant at the <0.05 level key secondary endpoints days in ICU and days on mechanical ventilation will be tested using the Holm step-down procedure. In this way an overall type 1 (false-positive) error rate of 5% will be maintained so that no statistical significance for the key secondary efficacy endpoints will be claimed unless the principal analysis of the primary efficacy endpoint using the ITT set is statistically significant at the 5% level.

Holm procedure will be applied as follows:

1. If the p-value for primary endpoint ≥ 0.05 then testing will stop and key secondary endpoints will not be tested. If p-value <0.05 then testing continues to key secondary endpoints.
2. P-values for key secondary endpoints will be sorted from smallest to greatest (ascending order).
3. The smallest p-value for key secondary endpoints will be compared to 0.025.
4. If the smallest p-value yields significant result at 0.025 level then sequential testing continues to the next largest p-value and adjusted alpha value of 0.05. Otherwise the testing will stop.

Data from all analyses, regardless of the level of significance, will be presented for review.

Controlled Quality Management Document	
	Sponsor: Veru Inc.
	Protocol Number: V3011902
STATISTICAL ANALYSIS PLAN. PHASE 2-3-4	

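### If mortality differs between arms as planned, the single-variance ANCOVA for the days endpoints gives standard errors about 9–18% too small and 95% intervals that cover about 89–93%.

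*SAP*

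**What the plan says.** SAP 6.11.5.2 defines the score and the model for days in ICU. On deaths: "For subjects who died the days in ICU will be set to 60". This applies even to a subject who died without entering the ICU. For survivors, if a "subject did not report any days in the ICU then their days will be set to zero except for those who died". The model is stated as "Treatment comparison will be based on analysis of covariance (ANCOVA) model including treatment as a factor, and study site (or country or region", followed by remdesivir, dexamethasone and the WHO randomization stratum. The output is a treatment difference with standard error, 95% confidence interval and p-value.

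The example PROC MIXED step has no REPEATED statement with GROUP= and no EMPIRICAL option, so one residual variance serves both arms. The option `ddfm=kr` adjusts degrees of freedom and small-sample bias; it does not relax that assumption.

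SAP 6.11.5.4 (mechanical ventilation) and 6.11.5.5 (hospital days) take over the same method. SAP 6.11.7 says that, once the primary endpoint is significant, "key secondary endpoints days in ICU and days on mechanical ventilation will be tested using the Holm step-down procedure". The one sensitivity analysis uses actual days, and for ventilation "and the same sensitivity analysis will be performed".

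Protocol 9.1 plans "140 subjects in the VERU-111 treated group and 70 subjects in the Placebo treated group" and sizes the trial "Assuming a rate of mortality of 5% in the VERU-111 treated group and 25% in the Placebo treated group".

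**The concern.** A score of 60 for death sits far from most survivors' values, so each arm's variance depends heavily on its mortality. If the drug lowers mortality as planned, the placebo arm becomes the more variable one. It is also half the size of the other arm. A pooled variance is weighted towards the larger, less variable arm, and so understates the uncertainty of the difference.

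Days in ICU and days on ventilation are the only secondary endpoints under multiplicity control, and they are tested only after mortality has been found to differ. Their intervals would therefore be reported mainly in the setting where the equal-variance assumption is least plausible. At stake is the stated precision of these results. The point estimate is not affected.

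**Working it through.** **Inputs.** n = 140 and 70; mortality 5% and 25% (Protocol 9.1); death = 60 and survivor never in ICU = 0 (SAP 6.11.5.2). The documents give no mean or SD for survivors' days, so the survivor mean m and SD s are assumed over a range, the same in both arms.

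**The plan's own figure.** Protocol 9.1 gives a 95% interval for the mortality difference. Its formula uses a separate variance per arm: SE = √(0.05×0.95/140 + 0.25×0.75/70) = √0.003018 = 0.0549, and −0.20 ± 1.96×0.0549 = [−0.308, −0.092]. This matches. The protocol's interval for mortality thus already allows unequal variances.

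**Variance of the days score in one arm.** v = (1−p)s² + p(1−p)(60−m)².

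If every survivor scores 0:
- VERU-111: 3600×0.05×0.95 = 171 (SD 13.1).
- Placebo: 3600×0.25×0.75 = 675 (SD 26.0). Ratio 3.95.
- Pooled variance: (139×171 + 69×675)/208 = 338.2. Model SE = √(338.2×(1/140 + 1/70)) = 2.69 days.
- Correct SE: √(171/140 + 675/70) = 3.30 days, which is 60×0.0549.
- SE ratio 2.69/3.30 = 0.817. Approximate coverage 2Φ(1.96×0.817)−1 = 89.1%.

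**Range over survivor assumptions, 5% against 25%.**

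| Survivor mean / SD | Variance ratio | Pooled SE | Correct SE | SE ratio | Coverage |
|---|---|---|---|---|---|
| 0 / 0 | 3.95 | 2.69 | 3.30 | 0.82 | 89.1% |
| 3 / 6 | 3.4 | 2.69 | 3.23 | 0.83 | 89.7% |
| 8 / 10 | 2.6 | 2.71 | 3.15 | 0.86 | 90.8% |
| 8 / 15 | 2.0 | 3.12 | 3.48 | 0.90 | 92.1% |
| 14 / 15.5 | 1.75 | 2.97 | 3.26 | 0.91 | 92.6% |

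The last row has 70% of survivors in ICU with mean 20 and SD 15: m = 0.7×20 = 14 and s² = 0.7×(225+400) − 196 = 241.5.

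**Other mortality rates in Protocol 9.1, same survivor range.** 10% against 25%: about 92–94%. 15% against 30%: about 93–94%. 15% against 20%: about 94%. 15% against 15%: variances equal, 95%. At 5% against 30%, close to Phase 2 ("VERU-111 treated group showed a 5.3% mortality rate compared to a 30% mortality rate in the Placebo group"), the first four rows give 88.6–91.8%.

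**With covariates.** The ANCOVA was simulated with treatment, site, remdesivir, dexamethasone and numeric WHO stratum, 4,000 runs per scenario. At 5% against 25%:

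| Survivors in ICU, mean days if in ICU | Model SE | Empirical SE | Coverage, pooled | Coverage, robust (HC3) SE |
|---|---|---|---|---|
| 40%, 8 | 2.65 | 3.12 | 90.4% | 95.7% |
| 40%, 20 | 2.96 | 3.33 | 91.7% | 95.1% |
| 60%, 15 | 2.76 | 3.15 | 91.8% | 95.1% |

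An arm-specific residual variance gave 94.8–95.4% in a separate set of runs. With equal mortality of 15% or 25% in both arms, the pooled test rejected 5.0% and 4.8% of the time.

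**The case against.** **Type I error.** A reader might infer that the Holm tests at 0.025 and 0.05 have an inflated false-positive rate. The documents do not support that. If the drug does nothing, the arms share one distribution and the pooled test rejects at about 5%. A false rejection with unequal variances needs equal mean days despite unequal mortality. At 5% against 25% with placebo survivors averaging 8 days, the placebo mean is 0.25×60 + 0.75×8 = 21, so VERU-111 survivors would have to average (21 − 3)/0.95 = 18.9 days. That is remote. This objection stands in full.

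**Conditionality.** A reader might also infer that the intervals are always too narrow, by a factor set by 171 against 675. Those variances hold only if no survivor has ICU days. The trial admits WHO 5 and 6 patients, including intubated ones, so some spread among survivors is certain. The problem also shrinks with the mortality gap and vanishes without one. This stands, and is why the result is a range.

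**Death score.** Protocol 9.5.1.1, 9.5.1.3 and 9.5.1.4 score deaths as 29 days, against 60 in the SAP; SAP section 9 does not list the change. With 29 and survivor mean 8, SD 10, the variances are 95 + 0.0475×441 = 115.9 and 75 + 0.1875×441 = 157.7, a ratio of 1.36 and coverage of about 94%. The size given here therefore rests on the SAP's score. The discrepancy is a separate matter that needs reconciling.

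**Mitigation.** SDs by arm will be tabulated, the code is labelled as an example, and the actual-days analysis drops the score of 60. None of this repairs the main interval: the text specifies an ordinary ANCOVA, and the sensitivity analysis changes the endpoint rather than the variance assumption.

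**Power.** A sponsor may prefer a conventional model that is valid under no effect and rejects more often. That is a real trade-off and belongs in the decision.

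**Conclusion.** The point holds for the situation the trial was designed for. At 140:70 and 5% against 25% mortality, with deaths scored as 60, the placebo arm is about 1.75 to 4 times as variable, the standard error is about 9–18% too small, and the nominal 95% interval covers about 89–93%. The mechanism and its direction follow from the documents; the size within that range depends on assumed survivor days. Ventilation days, where more survivors should score 0, probably lie nearer the upper end of the variance ratio.

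This is a miscalibration of standard errors and intervals, and of the p-values derived from them, when a treatment effect exists. It is not an error-rate failure of the Holm procedure, and it does not bear on the primary endpoint. It should be corrected, but it is not critical.

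**What to change.** In SAP 6.11.5.2, add `repeated / group=trt01pn;` to the PROC MIXED step, keep `ddfm=kr`, and state in the text that the ANCOVA estimates a separate residual variance for each arm. State that its standard error, interval and p-value are the ones used for days in ICU, days on mechanical ventilation (6.11.5.4), days in hospital (6.11.5.5) and the Holm step (6.11.7). Specify this before unblinding, so that the variance model is not chosen after seeing the arm SDs.

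The programming cost is one line of code and one or two sentences. The statistical cost is wider intervals: at 5% against 25% with all survivors at 0, the half-width goes from 1.96×2.69 = 5.3 to 1.96×3.30 = 6.5 days. In simulation, power at the 0.025 Holm threshold falls by about 5–8 percentage points, for example from 90% to 85% at 5% against 25%, and from 65% to 58% at 10% against 25%; the absolute levels depend on the assumed survivor days. That loss is the price of removing precision that the pooled model overstated. Endpoint, covariates and testing order stay as they are.

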#### 9.5.1.1 Days in ICU

Days in ICU will be summarized using descriptive statistics (n, mean, standard deviation, median, minimum, and maximum) by treatment group.

For subject who die, days in ICU will be set to the worst possible outcome (29 days) to give deaths unfavorable value in the analysis.

Treatment comparison will be based on analysis of covariance (ANCOVA) model including treatment as a factor and study site, gender, remdesivir use (No/Yes), dexamethasone use

(No/Yes) and WHO Ordinal Scale for Clinical Improvement at baseline as covariates. Treatment difference, standard error, 95% confidence interval and p-value will be presented.

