5 RANDOMIZATION

Controlled Quality Management Document		
	Sponsor:	Veru Inc.
	Protocol Number:	V3011902
STATISTICAL ANALYSIS PLAN. PHASE 2-3-4		

Randomization will be stratified by baseline WHO Ordinal Scale score of 4, 5 and 6 such that subjects with a WHO Ordinal Scale of 4, 5 and 6 at baseline are approximately equally distributed between the treatment groups.

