(no/yes, populated as ‘no’ for subjects who were not discharged from the hospital prior to withdrawing from the study before Day 60), DISCONT is whether subject discontinued treatment early (no/yes), REMDESIVIR is the use of remdesivir at baseline (no/yes), DEXAMETHASONE is the use of dexamethasone at baseline (no/yes) and WHOSTRATA is the WHO Ordinal Scale strata used in randomization. If the imputation model does not converge when both DISCHARGE and DISCONT variables are included then will be checked if either of them alone can be included in the model. If model converges with DISCHARGE or DISCONT alone but the model with both DISCHARGE and DISCONT does not converge, then imputation model will include only DISCHARGE.

The imputed data sets will be analyzed separately for each imputation using the logistic regression model. If all subjects have the mortality status at Day 60 then the imputation part above will not be used and observed data will be analyzed as such. Example SAS code for logistic regression is as follows:

```
proc logistic data=imputed1 order=internal descending;
by _imputation_;
class imputedresponse treatment sex site remdesivir dexamethasone whostrata
  / param=glm;
model imputedresponse = treatment sex site remdesivir dexamethasone whostrata
  / clodds=both firth;
estimate 'Treatment A vs. Treatment B' treatment 1 -1 / cl e exp;
lsmeans treatment / cl exp diff;
ods output modelanova=imputed_modelanova1
  lsmeans=imputed_lsmeans1
  diffs=imputed_diffs1
  parameterestimates=imputed_parmest1;
run;
```

If there are enough deaths to perform analysis without FIRTH option then it might be dropped out. Note that variable _IMPUTATION_ identifies each of the imputations created by PROC MI.

Finally, results from individual imputations are pooled via Rubin’s rules using PROC MIANALYZE. Example SAS code for pooling log(odds) for each treatment group is as follows:

```
proc mianalyze data=imputed_lsmeans1;
by trt01pn;
modeleffects estimate;
stderr stderr;
ods output parameterestimates=combined_odds1;
```

run;

Example SAS code for pooling log(odds ratio) for each treatment group is as follows:

```
proc mianalyze data=imputed_diffs1;
  modeleffects estimate;
  stderr stderr;
  ods output parameterestimates=combined_diffs1;
run;
```

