6.11.3 Secondary Analyses for the Primary Endpoint

The primary endpoint, mortality rate at Day 60, will also be assessed in the subset of mITT patients and Safety Analysis Set (all treated subjects).

Additionally, similar analysis to primary analysis will be performed in subgroups for region, standard of care, WHO Ordinal Scale at baseline and vaccination status.

To obtain risk differences between treatment groups, the same analysis as described above for primary efficacy analysis will be performed except identity link function will be used. Example SAS code is as follows:

```
proc genmod data=a order=internal;
class treatment sex site remdesivir dexamethasone whostrata;
model response=treatment sex site remdesivir dexamethasone whostrata
  / type3 dist=bin link=identity;
lsmeans treatment / e diff exp cl;
run;
```

Additionally, mortality rates will be summarized using Kaplan-Meier (KM) survival curves and equality of treatment groups will be tested using log-rank test. Hazard ratios will be calculated using the Cox proportional hazards model including terms for treatment, gender, study site (or country or region), remdesivir use (No/Yes), dexamethasone use (No/Yes) and WHO Ordinal Scale strata used in randomization. Any subjects for whom survival status is not available at day 60 will be censored at the day of their last observed assessment or last captured event.

Example SAS code for log-rank test is as follows:

```
proc lifetest data=XXX outsurv=surv1
  plots=survival(atrisk=0 to 60 by 1);
time time*cens(1);
strata treatment;
run;
```

Example SAS code for proportional hazards model is as follows:

```
proc phreg data=XXX;
class treatment sex site remdesivir dexamethasone whostrata;
model time*cens(1)=treatment sex site remdesivir dexamethasone
  whostrata;
```

Controlled Quality Management Document		
	Sponsor:	Veru Inc.
	Protocol Number:	V3011902

```
hazardratio treatment;  
assess ph / resample seed=1234;  
run;
```

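### The SAP's ANCOVA for days in ICU and days on ventilation drops the protocol's gender term without saying so, and its code fits the WHO stratum as a straight line

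*SAP*

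**What the plan says.** Randomization has three strata. SAP section 5 states: "Randomization will be stratified by baseline WHO Ordinal Scale score of 4, 5 and 6".

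For days in ICU, Protocol 9.5.1.1 specifies an ANCOVA with "treatment as a factor and study site, gender, remdesivir use (No/Yes), dexamethasone use" and the baseline WHO score. It lists the WHO score among the covariates without saying whether it is a category or a number.

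SAP 6.11.5.2 describes the same ANCOVA as "including treatment as a factor, and study site (or country or region), remdesivir use (No/Yes", followed by dexamethasone use and the WHO strata used at randomization. Gender is not in that list. The example PROC MIXED code has the CLASS statement "class trt01pn site remdesivir dexamethasone" and the MODEL statement "model response=trt01pn site remdesivir dexamethasone whostrata".

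Other SAP models are written differently. The primary logistic regression (6.11.1) uses "class imputedresponse treatment sex site remdesivir dexamethasone whostrata". The risk-difference and Cox models (6.11.3) use "class treatment sex site remdesivir dexamethasone whostrata".

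Days on mechanical ventilation, days in hospital and change in viral load all refer back to the days-in-ICU model (SAP 6.11.5). SAP 6.11.7 makes days in ICU and days on ventilation the two endpoints of the Holm procedure, tested at 0.025 and then 0.05 if the primary endpoint succeeds. SAP section 9 lists three changes from the protocol: the strata, the WHO-score analysis and the Holm procedure. Removing gender is not among them.

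**The concern.** There are two separate departures.

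- **Gender.** The protocol names it for this analysis and the SAP leaves it out of both text and code without explanation. Someone working from the protocol and someone working from the SAP would compute different p-values for endpoints that carry formal alpha.
- **WHO stratum.** In PROC MIXED, a numeric variable outside CLASS is fitted as a single slope. If the variable is stored as character, the step fails. A slope does not match a three-level stratified design or the SAP's other models.

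Equal steps are doubtful here. The SAP scores every death as 60 days, so the strata means are driven largely by mortality. Protocol 3.3 reports that all seven Phase 2 deaths had a baseline score of 5 or more, which points to a jump between 4 and 5. A line that misses this leaves between-stratum variation in the residual and widens the confidence interval. On gender, Phase 2 had 85% men on placebo against 53% on VERU-111. A similar chance imbalance would go unadjusted.

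**Working it through.** The plan gives no figure for this point, so the check is a comparison of specifications followed by a simulation of the effect.

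**1. Specifications side by side**

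| Place | Gender | WHO stratum |
|---|---|---|
| Protocol 9.5.1.1 | named | covariate, form not stated |
| SAP 6.11.5.2, text | absent | randomization strata, form not stated |
| SAP 6.11.5.2, code | absent from CLASS and MODEL | in MODEL, not in CLASS |
| SAP 6.11.1, code | in CLASS and MODEL | in CLASS and MODEL |
| SAP 6.11.3, code (risk difference, Cox) | in CLASS and MODEL | in CLASS and MODEL |

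**2. What the slope imposes**

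Factor form: E(Y) = μ + τT + β5·I(W=5) + β6·I(W=6). 
Linear form: E(Y) = μ + τT + βW, which forces β6 = 2·β5.

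The contribution of deaths to a stratum mean is 60 × mortality. Protocol 3.3 gives 46% Phase 2 placebo mortality for scores of 5 or more, pooled. Taking 2% at score 4, 46% at 5 and 60% at 6 (the 2% and 60% are assumptions) gives 1.2, 27.6 and 36.0 days. The steps are 26.4 and 8.4 days. With 50% at score 6 the second step is 30.0 − 27.6 = 2.4 days. Neither is close to equal.

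**3. Effect on the test**

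From the documents: 210 subjects, 2:1 within stratum, deaths scored 60. Assumed: strata shares 40/45/15%, 65% men, death odds ratio 0.4 when the drug works, and skewed ICU stays for survivors that depend on stratum. Gender either has no effect on death, or multiplies the odds by 1.4 in men and divides them by 1.4 in women. Site, remdesivir and dexamethasone are left out. Each scenario has 2,000 trials, with all models fitted to the same data and tested at two-sided 0.05. Pairs in a cell are without / with the gender effect.

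| Assumed mortality at 4/5/6 | Steps from deaths (days) | Power, SAP code | Power, corrected | Size, SAP code | Size, corrected |
|---|---|---|---|---|---|
| 15/35/60% | 12, 15 | 64.7 / 65.1% | 64.7 / 65.8% | 5.5 / 4.9% | 5.3 / 5.3% |
| 10/55/60% | 27, 3 | 62.2 / 63.5% | 64.1 / 65.3% | 4.0 / 4.5% | 5.2 / 5.5% |
| 10/12/70% | 1.2, 34.8 | 39.5 / 40.0% | 45.6 / 46.2% | 3.4 / 3.5% | 4.8 / 5.0% |

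Model standard error, linear over factor stratum, no gender effect:

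- 15/35/60%: 3.511/3.510 = 1.00 under no drug effect, 3.171/3.168 = 1.00 under effect
- 10/55/60%: 3.497/3.366 = 1.04 and 3.316/3.223 = 1.03
- 10/12/70%: 3.007/2.777 = 1.08 and 2.663/2.445 = 1.09

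The empirical spread of the treatment estimate hardly differs between the two forms (3.303 against 3.304, and 2.755 against 2.759, in the two non-linear patterns under no effect). Balanced allocation within strata already protects the estimate. The linear term only inflates the reported standard error, which is why size falls below 5%.

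A separate set of 3,000 trials per scenario at 2/46/50–60% mortality gave a standard error 1 to 4% larger with the linear term, size 3.9–4.0% against 4.4–4.9%, and power 1 to 2 points lower.

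**4. Gender alone**

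With the stratum as a factor, adding gender moved power from 65.1% to 65.8% at most, and otherwise by 0.2 points or less. With the stratum linear, the largest change was 40.0% to 40.8%.

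**The case against.** The code is labelled as an example and, as it reads, its ODS OUTPUT line has no closing semicolon, so it is not production code. The text refers to the randomization strata and nowhere asks for a line. Since the other models class the variable, this may be a slip that the programmer would have corrected. The linear term also does not contradict Protocol 9.5.1.1, which says nothing about its form. Protocol 3.3 adds that the Phase 2 gender imbalance was examined as a covariate and did not significantly affect the conclusions. The Phase 2 data pool scores 5 and 6, so the second step is unknown. The largest power loss needs a pattern that no figure in the documents supports. The primary endpoint is untouched.

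Most of this stands as a limit on size. The WHO half is a departure from the design and from the SAP's own practice, not from explicit protocol wording, and it may well be a slip. But the code is the only place where the form of the term is shown. The gender omission is in the text as well as the code, so it cannot be put down to illustrative code, and it does contradict the protocol.

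**Conclusion.** The concern holds and is minor. SAP 6.11.5.2 omits a protocol-specified covariate without declaring it, and its code fits a three-level stratum as a slope, in a model that serves both Holm-tested endpoints. There is no bias. The cost is a reported standard error that ranges from unchanged (near-equal steps) through 1 to 4% larger (mortality close to the Phase 2 figures) to about 9% larger (an extreme pattern). The matching power losses are about 0, 1 to 2 and 6 points. The test becomes conservative, not liberal. Omitting gender costs less than 1 point of power; there the issue is agreement between the two documents. These sizes rest on assumed stratum shares, death rates and ICU stays, and on a model without site, remdesivir or dexamethasone.

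**What to change.** In SAP 6.11.5.2:

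- CLASS: `class trt01pn sex site remdesivir dexamethasone whostrata;`
- MODEL: add `sex` to the right-hand side.
- Text: add gender to the covariate list and say that the WHO stratum is a three-level factor.
- Close the ODS OUTPUT line with a semicolon.

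Ventilation, hospital days and viral load then pick up the correction by reference. If gender was left out on purpose, keep the model, but declare and justify the change in section 9.

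The cost is a few words, 2 degrees of freedom (one for the stratum, one for gender) and a new SAP version, with no effect on data collection or sample size. It should be done before treatment codes are opened. If they already have been, report both models and label which document each follows.
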